# 9.2 Postoperative Adverse Events

- Chronic pain in the study eye present at 3 months postoperatively or later
- Flat anterior chamber with lens/cornea touch
- Shallow chamber with peripheral iridocorneal apposition
- BCVA loss of 3 Snellen lines compared to baseline at 3 months postoperatively or later
- Hypotony (defined as IOP < 6 mmHg) at 1 month postoperatively or later
- Maculopathy
- Hypotonic maculopathy
- CyPass obstruction causing an untoward effect in the study eye
- CyPass malposition
- CyPass migration, causing an untoward effect in the study eye
- Wound dehiscence
- Persistent anterior chamber cell and flare requiring steroid treatment after 2 months postoperatively
- Endophthalmitis
- Cataract formation or progression outside of expected progression
- Persistent hyphema present at 1 week postoperatively or later
- Corneal opacification, or corneal decompensation
- Significant corneal edema
- Retinal complications (dialysis, flap tears, retinal detachment, or proliferative vitreoretinopathy)

- Choroidal hemorrhage or choroidal effusion, defined as a choroidal effusion or detachment with at least a partially hemorrhagic component that obstructs vision or causes pain (including both peripheral and "kissing" choroidal detachments) lasting longer than 1 month
- Significant elevation in IOP requiring non-medical intervention
- Other events resulting in unplanned ocular surgical reintervention (other than paracentesis to relieve pressure prior to 1 week postoperative or Nd:YAG laser procedure for treatment of posterior capsular opacification)
- Loss of eye
- Significant ptosis
- Atrophy/phthisis
- Significant foreign body sensation at or after 3 months postoperative
- Increase in C:D ratio of  $\geq 0.3$  units on slit lamp biomicroscopic examination
- Confirmed increase in visual field loss outside of expected progression

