1.3 Randomization

Subjects were randomized to their assigned treatment on the day of their surgical procedure. Randomization lists were provided for each study site.

During the Dose Selection Phase of the study, subjects were randomized in Cohort 1 using a 1:1:1 schedule to receive either CyPass Micro-Stent with 30 μ l of adjunct Healon viscoelastic, CyPass Micro-Stent with 60 μ l of adjunct Healon viscoelastic, or the CyPass Micro-Stent with no adjunct Healon viscoelastic.

During the Expansion Phase of the study, subjects were randomized in Cohort 2 using a 1:1 schedule to receive either CyPass Micro-Stent without adjunct Healon viscoelastic or the CyPass Micro-Stent with 60 µl of adjunct Healon 5 viscoelastic.

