2.2 Safety Analysis Set

Safety analyses will be conducted using the safety analysis set on a treatment-emergent basis. The safety analysis set will include all enrolled subjects who undergo CyPass implantation surgery. For treatment-emergent safety analyses, subjects/eyes will be categorized under the actual treatment received. Therefore, subjects/eyes exposed to an incorrect study treatment will be included in the group corresponding to the actual treatment received. All listings of safety data will use the Safety Set.

3 Statistical Methods

Statistical analyses will be performed to summarize the primary and secondary efficacy endpoints as well as key safety evaluations. Additionally, within each treatment, changes from baseline will be assessed where appropriate.

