3.1 General Reporting Conventions

- Only one eye per subject may be treated under the study protocol. If both eyes qualify
 for the study, the study investigator will choose which eye will be the study eye.
 Unless specified otherwise, all ocular results refer to the study eye only. Therefore,
 throughout this SAP and corresponding tables and data listings, the number of
 subjects and eyes are synonymous.
- Available data at each assessment time point will be presented. No imputations will be made for missing data.

Document: TDOC-0053376 Version: 2.0; Most-Recent; Effective; CURRENT

Status: Effective

- Appropriate descriptive statistics will be computed and displayed by assessment time point for both continuous and categorical variables. For continuous variables, descriptive statistics include n (number of subjects/eyes) with non-missing data, mean, standard deviation (SD), median, minimum and maximum values. For categorical parameters, the number and percentage of subjects/eyes within each category will be presented. The denominator for percentages will be based on the number of subjects with non-missing data appropriate for summary purposes. Unless otherwise noted, percentages will be presented to one decimal place. Any confidence intervals (CI) will be at the alpha = 0.05 (two-sided) level.
- Summary tables will be presented by treatment and overall, as appropriate, for both phases/cohorts combined.
- Study day: Study day will be calculated relative to the date of stent implantation surgery (Day 0) as: Date of event – date of surgery. This formula will be used when calculating days to a specific event (i.e., ocular medications and/or AE start date). A negative study day indicates an event prior to surgery.
- Individual data listings of select data represented on the eCRF will be provided to facilitate investigation of the tabulated values and to allow for clinical review of key variables. All data listings will be sorted by Treatment (i.e., CyPass, CyPass with 30 μl, and CyPass with 60 μl), Cohort (1 or 2), site-subject number, visit, and assessment time points where appropriate. Data from unscheduled visits will be excluded from the summary tables (except for adverse events) but included, chronologically, in the data listings.
- Analyses will be generated using SAS® version 9.2 or higher.

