4.3 Demographic and Baseline Information, and General Medical and Ophthalmic History

Demographic and baseline information will be summarized using the FAS by treatment and overall. Subject demographics include age, sex, race, and ethnicity. Baseline information includes study eye (OD, OS) and lens status (phakic, pseudophakic).

General medical history findings and ophthalmic medical/surgical history findings will be presented separately in the data listings.

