6.3 Statistical Methods for Safety Analyses

6.3.1 Adverse Events

The applicable definition of an Adverse Event (AE) can be found in the study protocol. All AEs occurring from when a subject signs informed consent to when a subject exits the study will be accounted for in the reporting. A treatment emergent AE (TEAE) is an event on or after the day of surgery.

Document: TDOC-0053376 Version: 2.0; Most-Recent; Effective; CURRENT

Status: Effective

An overall summary of treatment emergent adverse events will be provided including the number and percentage of unique subjects with at least one AE, serious adverse event (SAE), AE leading to withdrawal, non-ocular or ocular, and study eye ocular event. Further, within study eye ocular events, the number and percentage of eyes with at least one: serious ocular event, intraoperative or postoperative ocular event, device related ocular event (definitely, probably, or possibly), serious device related, and serious device related leading to withdrawal. Additionally, for all eyes in the safety set, summarization of unique counts and percentages of ocular AEs by group will be provided separately for intraoperative or postoperative events by the in-house AE coded terms by descending frequency (sorted using overall group frequencies).

All reported adverse events will be detailed in the data listings. Individual subject listings provided will include:

- Ocular AEs for all eyes in the Safety Analysis Set
- Ocular AEs for all eyes not in the Safety Analysis Set
- Non-ocular AEs for all enrolled subjects
- Listing of deaths for all enrolled subjects

These listings will also include AEs that occur after signing the ICF but prior to surgery, if applicable.

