6.3.6 Slit Lamp Examination

The number and percentage of eyes in each category for assessing corneal edema, anterior chamber cells, anterior chamber flare, and other (slit lamp other specify), as well as lens status and opacity will be presented for each assessment visit.

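### The cataract adverse-event percentage is taken over all implanted eyes, so it understates the risk in phakic eyes; a row with a phakic denominator should be added

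*SAP*

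**What the plan says.** **Denominator.** SAP 6.3.1 describes the ocular adverse-event tables by coded term: "for all eyes in the safety set, summarization of unique counts and percentages of ocular AEs by group will be provided separately" for intraoperative and postoperative events. SAP 2.2 defines the set without regard to the lens: "The safety analysis set will include all enrolled subjects who undergo CyPass implantation surgery". Each subject has one study eye, so eyes and subjects coincide (SAP 1.2 and 3.1).

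**Event.** Protocol 9.2 lists among the anticipated postoperative events "Cataract formation or progression outside of expected progression".

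**Lens status.** Protocol 6.2 excludes aphakia but not pseudophakia, and SAP 4.3 summarises baseline lens status as phakic or pseudophakic. Protocol 9.2 also makes an exception for the "Nd:YAG laser procedure for treatment of posterior capsular opacification", a secondary sign that eyes with an artificial lens were foreseen.

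**Nearby provisions.** The general rule in SAP 3.1 is: "The denominator for percentages will be based on the number of subjects with non-missing data appropriate for summary purposes". For the slit-lamp tables, SAP 6.3.6 adds: "as well as lens status and opacity will be presented for each assessment visit". SAP 1.3 describes 1:1:1 and then 1:1 randomization from site lists and names no stratification by lens status. SAP 6.2 says that there are no formal safety hypotheses.

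**The concern.** The population mixes eyes that can develop cataract with eyes that cannot, and the table divides by both. The printed cataract percentage therefore depends on two things: the risk in phakic eyes, and how many pseudophakic eyes happened to enrol. A reader who wants to know the risk to a patient with a natural lens would take too low a figure from the table.

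The safety assessment is descriptive, so these percentages carry its conclusions. For most listed terms every implanted eye is at risk and the all-eyes denominator is the natural one. For cataract it is not.

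**Working it through.** **1. Is there a figure to reproduce?** No. The documents give neither a cataract rate nor a phakic share. The only design count is 43 eyes per arm (SAP 7), which is the month-12 completer number for the efficacy comparison and not the safety denominator.

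**2. Effect of the denominator.** Let N be the implanted eyes in an arm, p the phakic share and r the cataract risk in phakic eyes. Expected events are r × p × N, so:

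- tabulated rate: t = r × p
- at-risk rate relative to the tabulated one: r / t = 1 / p
- relative understatement: (r − t) / r = 1 − p, the pseudophakic share

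Both p and r in this table are assumed:

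| Phakic share p | 1/p | Shown if r = 10% | Shown if r = 20% |
|---|---|---|---|
| 30% | 3.3 | 3% | 6% |
| 50% | 2.0 | 5% | 10% |
| 70% | 1.4 | 7% | 14% |

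**3. Does another provision change the denominator?**

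- SAP 3.1 drops missing data. A pseudophakic eye's adverse-event status is not missing, and the specific wording of 6.3.1 governs.
- SAP 4.3 gives phakic counts by arm, but on the FAS, which SAP 2.1 groups by randomized treatment. Adverse events are grouped by treatment received (SAP 2.2). The two agree if nobody received the wrong treatment.
- SAP 6.3.6 shows lens status and opacity by visit, on the safety set (SAP 6.1). It gives no adverse-event rate in eyes at risk.

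**4. How far could arms differ through lens status alone?** Tables pool the cohorts (SAP 3.1). With 63 subjects in Cohort 1 and up to 90 in Cohort 2 (SAP 1.2), each main arm has at most about 63/3 + 90/2 = 21 + 45 = 66 eyes.

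- At 50% phakic, the 95% limit for the chance difference in phakic share is 1.96 × √(2 × 0.25 / 66) = 0.171, about 17 points.
- The hypergeometric 95% range is 27 to 39 pseudophakic eyes in an arm, a difference of 12/66 = 18 points.
- At that limit, with r = 10% in both arms, the table shows 10% × 39/66 = 5.9% against 10% × 27/66 = 4.1%.
- With 30% pseudophakic, the limit is 15 against 25 eyes: 10% × 51/66 = 7.7% against 10% × 41/66 = 6.2%.
- The chance of a difference of 10 points or more in lens status is about 18% (30% pseudophakic) to 22% (50%).

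For scale, the 95% sampling margin on the first pair is 1.96 × √((0.059 × 0.941 + 0.041 × 0.959) / 66) = 0.074, or 7.4 points. The gap due to lens status is 5.9 − 4.1 = 1.8 points.

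**The case against.** The strongest reply is that nothing here is wrong. Events per implanted eye is the usual form of an adverse-event table and a correct incidence for the treated population, and the SAP never labels it a risk in phakic eyes. This stands: the figure is incomplete for one term, not erroneous.

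The second reply is that the denominator is already planned output. Phakic counts by arm come from SAP 4.3, and lens status by visit from SAP 6.3.6. The FAS and the safety set both require implantation surgery, so they should hold nearly the same eyes. A reader can divide the cataract count by the phakic count. This stands as partial mitigation. It still leaves the reader to combine tables built on different grouping rules for a rate that the plan could print.

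A reader might also infer that the cataract rate will differ between arms because of lens status. The documents do not support that. Randomization makes the expected imbalance zero, a realised one would show in the SAP 4.3 table, and the calculation above puts the artefact at its 95% limit well inside ordinary sampling error. Nor should 43 per arm be used to widen that limit, since it counts month-12 completers. An illustration such as 60% against 40% phakic is a 20-point gap, beyond the 17-point limit at about 66 per arm.

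Finally, cataract is one of many listed events, has no endpoint status of its own, and counts only outside expected progression. This limits the weight of the point but does not change the denominator.

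**Conclusion.** The point holds as a limited one. Under SAP 6.3.1 the cataract percentage is valid per implanted eye, but it understates the risk in phakic eyes by a relative amount equal to the pseudophakic share. The direction follows from the text. The size does not: the factor of 3.3 to 1.4 rests on an assumed 30% to 70% phakic. A chance imbalance in lens status could add a modest distortion to the descriptive comparison between arms. No test or decision rule is affected, because SAP 6.2 sets no safety hypotheses. The existing lens outputs reduce the problem without removing it.

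Two assumptions remain. About 66 eyes per main arm is the planned maximum. The event list and eligibility come from protocol version D, while the SAP cites version F, so they are taken as unchanged; the lens categories in SAP 4.3 support this for eligibility.

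This is a cheap improvement worth making, not a flaw that undermines the safety analysis.

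**What to change.** In SAP 6.3.1, keep the all-eyes row for cataract formation or progression. Add a second row beneath it whose denominator is eyes phakic at baseline in the safety set, by treatment actually received, with the phakic n printed for each group. Defining the denominator at baseline also keeps in any eye whose lens is removed during follow-up.

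The cost is one table row and a flag from lens status already collected. The displayed cataract rate will be higher, which the sponsor should expect and the row label should explain. A device-related version of the row, and a shift table of lens opacity from baseline for the same eyes in SAP 6.3.6, would be useful but are optional.

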6.3.2 Manifest Refraction

All manifest refraction results (i.e., sphere (diopters), cylinder (diopters), and axis (degrees)) will be included in the data listings. Note, for cylindrical correction results (i.e., cylinder and axis) recorded in minus-cylinder notation will be converted to plus-cylinder notation for consistency in reporting.

Document: TDOC-0053376 Version: 2.0; Most-Recent; Effective; CURRENT

Status: Effective

6.3.3 Best Corrected Visual Acuity (BCVA)

The number and percentage of responses relative to each Snellen equivalent category (i.e., 20/20 or better, 20/25 or better, etc.) will be presented at each assessment visit. Results will also be included in the data listings.

6.3.4 Intraocular Pressure

Intraocular pressure (IOP) measurements will be recorded in mmHg and reported up to one decimal place. IOP measurements will be summarized relative to both medicated and unmedicated baseline assessments compared to postoperative visits as follows. For medicated baseline IOP, descriptive summaries of observed values, as well as change and percent change from medicated baseline (Baseline1) values will be presented at each postoperative assessment visit compared to medicated baseline. Similarly, descriptive

Document: TDOC-0053376 Version: 2.0; Most-Recent; Effective; CURRENT

Status: Effective

summaries of observed values, as well as change and percent change from unmedicated baseline (Baseline2) values will be presented at each postoperative assessment visit compared to unmedicated baseline.

Further, IOP measurements over time at the Screening, Baseline, 1 Mo, 3 Mos, 6 Mos, 12 Mos, and 12 Mos unmedicated assessments will be presented graphically using side-by-side box plots to compare results between the CyPass alone and CyPass with 60 µL groups.

6.3.5 Gonioscopy

All gonioscopy results will be included in the data listings.

6.3.6 Slit Lamp Examination

The number and percentage of eyes in each category for assessing corneal edema, anterior chamber cells, anterior chamber flare, and other (slit lamp other specify), as well as lens status and opacity will be presented for each assessment visit.

6.3.7 Visual Field

Visual field measurements will be conducted at Screening and 12 months postop. For subjects having both measurements relative to the Humphrey Visual Field Analyzer 24-2 SITA Standard test, descriptive summaries of observed and change from screening values for visual field mean deviation (dB) will be presented at each assessment visit. Also, a categorical summary of the changes from screening will be presented using the following three categories: Increase \geq 6.0 dB, No Change (-6.0 dB < to < 6.0 dB), or Decrease \geq 6.0 dB.

Listings will be provided for all subjects' visual field test results as three subsets below,

- Subjects with matched-pairs relative to Humphrey 24-2 SITA Standard results (This subgroup will match the summary table described above.);
- Subjects with matched-pairs relative to Octopus Normal test results; and
- All other subjects without matched-pairs relative to the same visual field test or missing an assessment for a visit.

Document: TDOC-0053376 Version: 2.0; Most-Recent; Effective; CURRENT

Status: Effective

6.3.8 Dilated Fundus Examination and C/D Ratio

The fundus examination will be conducted to identify any clinically significant fundus abnormalities, as well as measure the vertical cup to disc ratio (C/D ratio). The C/D ratio will be summarized descriptively at each assessment visit.

A listing will be provided which presents all subjects with any clinically significant fundus abnormalities, as well as present the C/D ratio results.

6.3.9 Secondary Surgical Interventions

A listing detailing subjects with secondary surgical interventions in the study eye will be provided. The listing will include the following variables: treatment, cohort, site-subject, age, sex, race, ethnicity, eye, surgery term, due to AE (if yes, specify), surgery date, study day, and existing condition (Y/N).

6.3.10 CyPass Explantation and/or Repositioning

A listing detailing subjects with CyPass explantation and/or repositioning will be provided. The listing will include the following variables: treatment, cohort, site-subject, age, sex, race, ethnicity, explantation or repositioning event, surgery date, study day, pre-IOP, pre-and post-Shaffer grades, and reason.

6.3.11 Device Deficiencies

The applicable definition of a device deficiency is in the study protocol. A listing of all device deficiencies, as recorded on the Device Deficiency Log, will be provided.

7 Sample Size and Power Calculations

The primary effectiveness endpoint is the outcome of \geq 20% decrease in IOP from baseline without IOP lowering medications up to 12 months post-operatively (IOP response). The proportion of eyes meeting the effectiveness outcome, IOP response rate, will be assessed at 12 months. A sample of at least 101 eyes will be enrolled across the two groups (CyPass only control and CyPass + Healon 5 dose selected) with an estimated 86 eyes completing their month 12 visit. Assuming a 30% success rate for the control eyes and a 60% success rate for the visco-assisted eyes, 80% power can be achieved with 43 eyes per arm using a two-tailed alpha of 0.05 that is based on the Likelihood Ratio Chi-square test for two proportions. It is

Document: TDOC-0053376 Version: 2.0; Most-Recent; Effective; CURRENT

Status: Effective

estimated that approximately 10% of those receiving the CyPass Micro-Stent may be lost to follow-up.

Document: TDOC-0053376 Version: 2.0; Most-Recent; Effective; CURRENT

Status: Effective

Date/Time (mm/dd/yyyy GMT):	Signed by:	Justification:
05/29/2017 11:06:02		
05/30/2017 18:23:03		
06/05/2017 20:12:51

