# 6. STUDY POPULATION

## 6.1 Inclusion Criteria

Individuals will be assessed for study eligibility based on the criteria presented below. Unless specified otherwise, ocular criteria refer to the study eye only.

- 1. 21 years of age or older, male or female.
- 2. Able to understand study requirements, willing to follow study instructions, provide written informed consent, and comply with all study requirements, including required study follow-up visits.
- 3. Diagnosis of OAG, including pseudoexfoliation glaucoma and pigmentary glaucoma, which meets diagnostic criteria defined below:
  - Vertical cup-to-disc ratio (C:D) on fundoscopic exam of at least 0.6, or
  - Heidelberg Retinal Tomograph (HRT) of good quality demonstrating a Moorfield Regression Analysis that is "outside normal limits", or
  - Optical Coherence Tomography (OCT) demonstrating a thinness of the nerve fiber layer at the p < 5% level as defined by the instrument's built-in age-adjusted normative database.
  - Glaucoma Visual Field (VF) with a Mean Deviation (MD) < 0 dB
- 4. Baseline unmedicated IOP of 21 mmHg 36 mmHg. *Note: Subjects who were using ocular hypotensive medication at the time of study enrollment must complete a required medication washout period prior to baseline IOP assessment as specified in Table 7.*
- Gonioscopy confirming normal angle anatomy at site of implantation, and Shaffer grade of ≥ III in at least two quadrants, one of which must be the quadrant of the intended site of implantation.

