5.1 Efficacy Endpoints

Primary Efficacy Endpoint

The outcome of \geq 20% decrease in IOP from baseline (unmedicated/Baseline2) up to 12 months post-operatively without IOP lowering medications (IOP response) is determined as follows,

Percent change in IOP from baseline is defined as, for each subject,

$$Percent \ Change = \frac{PostOperative \ IOP - Baseline \ IOP}{Baseline \ IOP} \ge 100$$

such that negative percent changes represent a favorable effect, while positive percent changes represent an unfavorable effect. Therefore, IOP response is achieved if the percent change is $\geq 20\%$ lower than baseline (i.e. the percentage change is $\leq -20\%$).

 IOP response rate: Proportion of eyes meeting the effectiveness outcome is defined as the number of eyes with occurrence of ≥ 20% decrease from baseline divided by the number of eyes having non-missing post-Baseline and Baseline IOP measurements at each the given visit.

While the IOP response rate at 12 months without IOP lowering medications is the primary endpoint, results will be summarized at each postoperative visit relative to unmedicated baseline. Note, at 12 months for subjects being treated with ocular hypotensive medications, a washout for the 12 month assessment was intended to obtain unmedicated IOP measurements. Note: prior to version D of the protocol, the 12 Month Washout visit was not required for the initial dose selection phase subjects who were on IOP lowering medication

Document: TDOC-0053376 Version: 2.0; Most-Recent; Effective; CURRENT

Status: Effective

Secondary Efficacy Endpoints

[figure not shown]
 Rate of intraoperative and post-operative device related ocular adverse events up to 12 months postoperatively

```
Rate = \frac{\text{\# of subjects who experience } either \text{ an intraoperative } and/or \text{ post} - \text{operative device related ocular AE}}{\text{\# of subjects}}
```

such that device related includes definitely, probably, or possibly.

- Mean change in medicated IOP from baseline (Baseline1) to 12 months postoperatively regardless of medications
 - Computed for subjects having both non-missing baseline medicated IOP and
 12 month postoperative regardless of medications measurements.
- Proportion of eyes using ocular hypotensive medications at 12 months postoperatively

```

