5.3 Statistical Methods for Efficacy Analyses

The primary efficacy endpoint, the achievement of a 20% decrease in IOP relative to baseline in the absence of IOP lowering medications up to 12 months post-operatively will be summarized at each post-operative visit by the number and percent of subjects having IOP response and the corresponding 95% confidence interval (CI) based on the exact binomial distribution.

[figure not shown]
Secondary efficacy endpoints describing proportions meeting given criteria will be summarized at each post-operative visit by the number and percentage of responses and the corresponding 95% CI based on the exact binomial distribution. While descriptive statistics for all continuous parameters for the actual values and change from baseline, including the 95% CI of the actual/observed results (based on a *t*-distribution) and change (based on a paired *t*-distribution), will be provided for each protocol specified visit, the 12 month visit is of most interest.

All efficacy analysis summaries will be produced using the FAS set.

Document: TDOC-0053376 Version: 2.0; Most-Recent; Effective; CURRENT

Status: Effective

Document: TDOC-0053376 Version: 2.0; Most-Recent; Effective; CURRENT

Status: Effective

6 Safety Analysis Strategy

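### The visible SAP specifies neither a between-arm analysis of Month 12 response nor adjustment for unmedicated baseline IOP; prespecifying both would cost little and could gain a few points of power

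*SAP*

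**What the plan says.** - **Sizing (SAP section 7).** The assumptions are "Assuming a 30% success rate for the control eyes and a 60% success rate for the visco-assisted eyes", and the plan concludes that "80% power can be achieved with 43 eyes per arm". The test behind that figure is described as "a two-tailed alpha of 0.05 that is based on the Likelihood Ratio Chi-square test for two proportions". This is the only between-arm test named in the public text, and it takes no covariate. Protocol 8.1 has the same sizing without naming a test.
- **Endpoint (SAP 5.1).** The outcome is a 20% "decrease in IOP from baseline (unmedicated/Baseline2) up to 12 months post-operatively without IOP lowering medications". Its denominator counts only eyes with both a baseline and a post-baseline IOP.
- **Analysis (SAP 5.3, Protocol 8.3).** The primary endpoint is summarised at each visit by count, percentage and a "95% confidence interval (CI) based on the exact binomial distribution" (Protocol 8.3 does not name the interval method). No test, interval for the difference, model or covariate is visible.
- **Baseline (SAP 3.2, Protocol 6.1).** Baseline2 is the IOP after washout, or the screening value for unmedicated eyes. Entry requires "Baseline unmedicated IOP of 21 mmHg 36 mmHg", read here as a range of 21 to 36 mmHg. That criterion comes from protocol Version D, whereas the SAP cites Version F.
- **Allocation (SAP 1.3, 1.4).** Randomisation used site lists, with no stratification by IOP described. The study was not masked.

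**The concern.** Baseline2 sets the fall in mmHg that an eye needs to count as a responder, and it is available for every eye in the denominator. With 43 eyes per arm and no described stratification on it, the arms can differ in baseline IOP by chance. If response depends on baseline, that difference feeds into the unadjusted contrast, and some explainable variation stays in its standard error.

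The remedy has to be written in advance. In an unmasked trial, a covariate chosen after the results are seen would carry little weight.

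**Working it through.** **1. The plan's own figure.** For the likelihood-ratio chi-square, the noncentrality is λ = 2n Σ[p ln(p/p̄) + (1−p) ln((1−p)/(1−p̄))], with p̄ = 0.45.
- Control: 0.3 ln(0.3/0.45) + 0.7 ln(0.7/0.55) = 0.0472
- Visco-assisted: 0.6 ln(0.6/0.45) + 0.4 ln(0.4/0.55) = 0.0452
- λ = 2 × 43 × 0.0924 = 7.95, and power ≈ Φ(√7.95 − 1.96) = Φ(0.859) = 80.5%

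At 42 per arm power is 79.6%, so 43 is reproduced exactly.

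**2. When response depends on baseline.** The required fall is 0.20 × 21 = 4.2 mmHg and 0.20 × 36 = 7.2 mmHg. Write postoperative IOP as a + bB + e, where B is Baseline2. An eye responds when a + bB + e ≤ 0.8B, that is, when e ≤ (0.8 − b)B − a. Each extra mmHg of baseline therefore adds 0.8 − b mmHg of margin: 0.6 at b = 0.2, 0.4 at b = 0.4, 0.2 at b = 0.6 and none at b = 0.8. The dependence disappears only near b = 0.8.

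**3. Assumptions.** None of these is in the documents: baseline mean 25.5 and SD 3.0 before truncation to 21–36 (about 2.7 after), residual SD 3.5 to 4.5 mmHg, and slope b varied. Response rates are held at 30% and 60%.

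**4. Size of chance imbalance.** The standard error of the difference in mean baseline is 2.7 × √(2/43) = 0.58 mmHg. In simulation at b = 0.2 to 0.4, each 1 mmHg of imbalance moves the unadjusted difference by 3.4 to 6.1 points, and by at most 0.6 points after adjustment. A one-standard-error imbalance therefore moves the unadjusted difference by 3.4 × 0.58 = 2.0 to 6.1 × 0.58 = 3.5 points.

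**5. Hand check on the variance.** The unadjusted variance is (0.3 × 0.7 + 0.6 × 0.4)/43 = 0.01047. The share due to imbalance is (0.034 × 0.58)²/0.01047 = 3.7% up to (0.061 × 0.58)²/0.01047 = 12%, before the small cost of estimating a coefficient.

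**6. Simulation, 43 per arm.** Unadjusted and logistic-standardised risk differences were compared for variance, and likelihood-ratio tests for power.

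| Slope b | Variance of risk difference | Power gain |
|---|---|---|
| 0.2 to 0.4 | falls about 4% to 10% | about 2 to 4 points |
| 0.6 to 0.8 | ratio 0.99 to 1.01 | about zero |

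Repeat runs at b = 0.2 to 0.4 spread around these values, with gains of 1.6 to 5.0 points and variance falls of 2% to 12%. Analytically, 7.95/0.96 and 7.95/0.90 give power of about 82.0% and 84.4%, which are gains of 1.6 and 3.9 points.

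**7. Cross-check with a different model.** Here the odds ratio for response per SD of baseline is fixed directly, with 12,000 trials per scenario.

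| Odds ratio per SD | Unadjusted power | Adjusted power |
|---|---|---|
| 1.0 | 80.6% | 81.1% |
| 1.5 | 81.0% | 83.1% |
| 2.0 | 80.7% | 85.0% |
| 3.0 | 81.2% | 89.0% |

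In the roughly 8% of trials with an imbalance above 0.3 SD against the treated arm, power goes from 70.2% to 82.3% at an odds ratio of 1.5, and from 62.5% to 84.2% at 2.0.

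**8. Null rejection.** Over slopes 0.2 to 0.8 the unadjusted test rejects in 4.5% to 5.8% of null trials and the adjusted test in 4.4% to 6.2%. The adjusted rate is higher by up to about 0.7 points.

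**The case against.** A reader might infer that the primary comparison is planned as an unadjusted test. The documents do not support that. SAP section 7 states a sizing basis, and sizing on an unadjusted test does not commit the analysis to one. The visible part of SAP 5.3 plans no between-arm comparison of either kind. The contents list has unlabelled entries between 5.1 and 5.3 and directly after 5.3, and no section 5.2 appears in the body. A hypothesis, test or model may be in the withheld text. This objection stands, so the point is limited to what is visible.

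The endpoint is also already scaled to each eye's baseline. The range of 4.2 to 7.2 mmHg only restates 20% of baseline and does not by itself show that response varies with it. This stands in part: scaling removes the dependence only if b is near 0.8. Eyes enter on a post-washout threshold, and the same reading is the denominator. Measurement noise and regression to the mean would therefore tend to flatten the slope. That makes a shallow slope plausible but does not establish one.

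Finally, adjustment is not entirely free. The adjusted likelihood-ratio test rejects slightly too often under the null. Its gain of 0.5 points when baseline has no prognostic value (odds ratio 1.0) is therefore not information. This stands, and is a reason to keep the unadjusted test alongside.

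**Conclusion.** The point holds as a worthwhile improvement and not as an error. The visible SAP names no between-arm analysis of the primary endpoint outside the sizing section and no use of Baseline2 as a covariate. At 43 eyes per arm, adjustment would cut the variance by about 4% to 10% and add about 2 to 4 points of power if the slope is 0.2 to 0.4 mmHg per mmHg. At 0.6 or above the gain is about zero. It would also largely remove the effect of a chance imbalance in baseline IOP, which has a standard error of about 0.58 mmHg if the baseline SD is about 2.7.

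These sizes rest on an assumed baseline distribution, residual SD and slope, none of which the documents give. A reader might conclude that power is being wasted or that the planned test is unsound. Neither follows: the loss may be nil, the unadjusted test is valid over repeated randomisation, and the stated 80% power is met.

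**What to change.** In SAP 5.3, prespecify the Month 12 comparison of 60 µl with CyPass alone:

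- **Main estimate:** logistic regression of response on treatment and continuous Baseline2 IOP, reported as a standardised (marginal) risk difference with a 95% CI, with the interval method stated.
- **Supportive analysis:** the unadjusted likelihood-ratio chi-square from section 7, which also guards against the slightly higher null rejection rate of the adjusted test.
- **Covariates:** fix the list in advance. If site or cohort is wanted, because of the site lists and the pooling of cohorts, justify and name it now.
- **Unchanged:** the responder definition and the per-arm exact intervals.

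If withheld text already specifies a between-arm comparison, add Baseline2 there.

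The cost is SAP wording and a few lines of code. No new data are needed, and no eyes are lost, because the response denominator already requires a baseline IOP. The one small downside is the null rejection rate described above.
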